4.4.2 Data Collection and Follow-up for Withdrawn Subjects

If a subject withdraws consent to participate in the study, for subject safety or other reasons, attempts will be made to obtain permission to collect follow up information whenever possible, including through medical chart review. As outlined in section 4.4.1, “When and How to Withdraw Subjects,” the exit visit will include those study assessments and procedures that would have been performed at the next scheduled visit. Although early withdrawal could be related to the safety profile of the study drug, it could also be related to other reasons, and thus follow-up assessments could be important in capturing both additional safety information as well as study outcomes that affect interpretation of risk versus benefit. Since the study drug will be given only once, long-term safety consequences related to participation are expected to be very limited.

5 Study Drug

5.1 Description

Study drugs (entolimod, diluent and placebo) are manufactured under current Good Manufacturing Practices (cGMP).

The study sponsor will provide entolimod as a liquid for IM injection in 2 mL prefilled, single-use vials containing 50 µg of entolimod in 0.5 mL (concentration of 100 µg/mL) of formulation. The formulation comprises phosphate-buffered saline (PBS) containing 0.1% polysorbate 80 (Tween 80).

For the dilution of 100 µg/mL entolimod the study sponsor will supply entolimod diluent in 50 mL single use vials filled with 40 mL of phosphate-buffered saline (PBS) containing 0.1% polysorbate 80 (Tween 80).

The study sponsor will also provide a matching placebo. The placebo has the same excipient composition as the active drug formulation (i.e., PBS containing 0.1% Tween 80) and fill-finished in the same type of 2 mL single use vials (0.5 mL per vial).

Vials of entolimod and placebo should be kept frozen at -70 +/- 10°C and -20 =/- 5°C until thawed for use. Entolimod contained in vials and stored at -70 +/- 10°C is stable for ≥ 7 years. The drug can withstand 3 freeze-thaw cycles. Entolimod should be thawed immediately before the dilution. Once thawed, study drug can be stored at 5° +/- 3°C for up to 8 hours. Entolimod dilutions should be completed within the established periods of stability for drug in the thawed vials. Diluted entolimod should be administered immediately after dilutions preparation.

5.2 Treatment Regimen

A single IM injection of study drug (entolimod or placebo) will be administered to each subject on the morning of vaccination, Day 1 (to be administered within 1 inch and within 1 minute of flu vaccine). The appropriate amount of study drug will be aseptically withdrawn from the required number of study drug vials into a 1-mL tuberculin syringe calibrated in 10-µL units. The drug will be administered from the syringe through a 22-25-gauge needle (see table 1 below) at a 90°-angle to the skin surface into the deltoid muscle between the acromion process and the midaxillary line.

Table 1. Needle size.

Female or Male up to 69 kg	22-25 gauge, 1 inch needle
Female 70 kg to 91 kg, Male 70 kg to 118 kg	22-25 gauge, 1 inch to 1.5 in needle
Female > 91 kg, Male > 118 kg	22-25 gauge, 1.5 inch needle

5.3 Method for Assigning Subjects to Treatment Groups

Study subjects will be randomized in a dose-escalated 4-arm study of entolimod in 3 possible doses or placebo (see table 2 below). Beginning in period 1, the first eight patients in the 1ug arm will be evaluated for safety and tolerability by the DSMB prior to the enrollment of the remainder of the 1ug arm. In addition, after review we will proceed with recruitment in period 2 of the 3ug arm. Again, safety and tolerability will be assessed in the first 8 patients of the 3ug arm during period 2. Similarly, after evaluation by the DSMB we will proceed with the remainder of the 3ug arm. In period 3 we will evaluate safety and tolerability in the first 8 subjects of the 10ug arm. An evaluation by the DSMB will be completed and we will proceed with the remainder of the 10ug arm until all subjects have been accrued. We will recruit the balance of the subjects remaining to be enrolled (to obtain 25 subjects per arm) pending safety review by the DSMB.

Randomization will be performed using Medidata Balance software, integrated into the electronic case report forms Medidata RAVE. A permuted block design will be used, with stratification by sex. Subjects and study center personnel involved in the care of subjects will be blinded to study drug assignment (entolimod vs. placebo).

Table 2. Dose-Escalated 4-arm Study

Arm	Placebo	1ug	3ug	10ug
Period 1	2	6		
Period 2	2		6	
Period 3	2			6

Dose Levels

Cohorts of subjects will be sequentially enrolled at progressively higher starting dose levels. The following dose levels are planned:

- Dose Level 1: 1 μ g
- Dose Level 2: 3 μ g
- Dose Level 3: 10 μ g

These doses are within the dose range of 1 μ g to 10 μ g and equal or greater than five times less than that which has been previously evaluated in healthy subjects and patients with advanced solid tumors.

5.4 Preparation and Administration of Study Drug

All dilutions of entolimod are performed in a biosafety cabinet under aseptic conditions by a licensed pharmacist on the day of injection. The drug dilution instructions for each dose level are described below and a summary of instructions is provided in Table 3.

Dose Level 1: 1 μ g of entolimod per injection

Using 10 cc syringe remove 8.7 mL of diluent from 50 mL diluent vial and transfer this aliquot into 10 mL empty sterile vial. Using 0.3 or 1 cc syringe remove 0.3 mL of entolimod from the drug product vial. Holding the vial with 8.7 mL of diluent upside down inject 0.3 mL of

entolimod solution directly into the diluent in the vial (dilution 1:30, final entolimod concentration 3.3 μ g/mL). Mix the vial by gentle rotation.

Dose Level 2: 3 μ g of entolimod per injection

Using 3 cc syringe remove 2.7 mL of diluent from 50 mL diluent vial and transfer this aliquot into 10 mL empty sterile vial. Using 0.3 or 1 mL syringe remove 0.3 mL of entolimod from the drug product vial. Holding the vial with 2.7 mL of diluent upside down inject 0.3 mL of entolimod solution directly into the diluent in the vial (dilution 1:10, final entolimod concentration 10 μ g/mL). Mix the vial by gentle rotation.

Dose Level 3: 10 μ g of entolimod per injection

Using 1 cc syringe remove 1 mL of diluent from 50 mL diluent vial and transfer this aliquot into the vial of drug product containing 0.5 mL of 100 μ g/mL entolimod (dilution 1:3, final entolimod concentration 33.3 μ g/mL). Mix the vial by gentle rotation.

Table 3. Dilution of 100 μ g/mL Entolimod for IM Injections.

Dose level, μ g	Diluent volume, mL	100 μ g/mL entolimod volume, mL	Diluted entolimod volume, mL	Dilution factor	Diluted entolimod concentration, μ g/mL	Injection volume, mL	Number of injection syringes that can be filled
1	8.7	0.3	9	30	3.3	0.3	up to 26
3	2.7	0.3	3	10	10	0.3	up to 6
10	1	-	1.5	3	33.3	0.3	up to 4

Placebo group

Remove 0.3 mL of placebo from placebo vial using 1 cc syringe.

Subjects will receive a single dose of study drug in the form of an IM injection. This injection is to be administered in the upper arm within 1 inch of the injection site of the influenza vaccine.

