1.2 Investigational Agent

Entolimod is provided as a sterile, clear, colorless or slightly yellow liquid for IM injection. The drug is supplied in 2 mL Type 1 DIN 2R glass vials secured with V35 bromo-butyl injection stoppers and sealed with aluminum white flip off caps. Each single-use vial is prefilled with 50 μ g of entolimod in 0.5 mL (concentration of 10 μ g/100 μ L). Entolimod diluent comprises sodium chloride (8.0 mg/mL), potassium chloride (0.2 mg/mL), disodium hydrogen phosphate dehydrate (1.44 mg/mL), potassium dihydrogen phosphate (0.24 mg/mL), polysorbate 80 (Tween 80) (0.001 mL/mL), and water for injection (to 1 mL), with a pH of 7.4 \pm 0.5. The diluent is supplied in 50 mL vials with extractable volume 40 mL.

[figure not shown]
A matching placebo is also provided as a sterile, clear, colorless to slightly yellow liquid for IM injection in prefilled vials that are identical in appearance to the vials containing active drug. The placebo comprises of the same liquid used as a diluent for the active drug formulation.

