5.7 Packaging

Entolimod, placebo and diluent will be shipped under cold conditions to the site in cardboard boxes containing 10 single-use vials per box placed into foam inserts. Entolimod vials should remain in the boxes in which they are supplied or stored in a manner that prevents glass-to-glass contact.

Both packaging boxes and individual vials will be labeled with the liquid contents, date of manufacture, lot number, manufacturer information, storage requirements, Mayo Clinic's IRB number, the name of the PI and the federal investigational new drug use warning. See Figure 3.

Figure 3. Labels for Experimental Study Drug Vials and Secondary Shipment Packages.

Labels for entolimod vials

Solution for Injection 0.1 mg/mL Entolimod, 0.35 mL
 Date of Manufacture: 22 AUG 2011
 Lot Number: [REDACTED]
 Manufactured by: Wacker Biotech B.V. (former SynCo Bio Partners B.V. Amsterdam, Netherlands)
 Store at: -70°C
 Mayo Clinic IRB # 19-004847;
 [name]
Refer to Clinical Protocol for Dosing
Caution – New Drug Limited By Federal Law To Investigational Use

Labels for secondary entolimod package

Solution for Injection 0.1 mg/mL Entolimod, 0.35 mL
 Date of Manufacture: 22 AUG 2011
 Lot Number: [REDACTED]
 Manufactured by: Wacker Biotech B.V. (former SynCo Bio Partners B.V. Amsterdam, Netherlands)
 Store at: -70°C
 Mayo Clinic IRB # 19-004847;
 [name]
 Amount in Box: 10 vials
Refer to Clinical Protocol for Dosing
Caution – New Drug Limited By Federal Law To Investigational Use

Labels for entolimod placebo vials

Solution for Injection Entolimod Placebo, 0.35 mL
 Date of Manufacture: 18 AUG 2011
 Lot Number: [REDACTED]
 Manufactured by: Wacker Biotech B.V. (former SynCo Bio Partners B.V. Amsterdam, Netherlands)
 Store at: -70°C
 Mayo Clinic IRB # 19-004847;
 [name]
Refer to Clinical Protocol for Dosing
Caution – New Drug Limited By Federal Law To Investigational Use

Labels for secondary entolimod placebo package

Solution for Injection Entolimod Placebo, 0.35 mL
 Date of Manufacture: 18 AUG 2011
 Lot Number: [REDACTED]
 Manufactured by: Wacker Biotech B.V. (former SynCo Bio Partners B.V. Amsterdam, Netherlands)
 Store at: -70°C
 Mayo Clinic IRB # 19-004847;
 [name]
 Amount in Box: 10 vials
Refer to Clinical Protocol for Dosing
Caution – New Drug Limited By Federal Law To Investigational Use

Labels for entolimod diluent vials

Entolimod sterile diluent, 40 mL per single use vial
 Date of Manufacture: 25 MAR 2016

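### The protocol text gives a 0.5 mL drug vial fill but the labels print 0.35 mL unexplained; only the 10 µg preparation depends on which figure is the fill

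*Combined protocol and SAP*

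**What the plan says.** Three sections give the drug vial volume as 0.5 mL.

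- Section 1.2: "Each single-use vial is prefilled with 50" µg in 0.5 mL.
- Section 5.1: a "liquid for IM injection in 2 mL prefilled, single-use vials containing 50" µg in 0.5 mL, at 100 µg/mL. The placebo is "fill-finished in the same type of 2 mL single use vials (0.5 mL per vial").
- Section 5.4, Dose Level 3: "remove 1 mL of diluent from 50 mL diluent vial and transfer this aliquot into the vial of drug product containing 0.5 mL".

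The labels in section 5.7 (Figure 3) differ. The entolimod vial and box labels read "Solution for Injection 0.1 mg/mL Entolimod, 0.35 mL", and the placebo vial and box labels read "Solution for Injection Entolimod Placebo, 0.35 mL". No label says whether this is a fill or an extractable volume. All four carry the line "Refer to Clinical Protocol for Dosing".

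Section 5.4 prepares the doses in two ways. Dose Levels 1 and 2 add a measured 0.3 mL of drug to 8.7 mL and 2.7 mL of diluent, and placebo is a measured 0.3 mL. Dose Level 3 adds 1 mL of diluent to the whole drug vial; Table 3 shows a dash for its drug volume and assumes 1.5 mL in total. Every injection is 0.3 mL.

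**The concern.** The text and the labels give different volumes for the same vial. The labels send the pharmacist to the protocol for dosing, and the protocol does not say what 0.35 mL means. The one preparation that takes its drug quantity from the vial content, without measuring it, is the top dose.

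If the label figure were the fill, the 25 subjects in the 10 µg arm would receive less than the dose under which their titers and adverse events are reported. Section 7.2 says the trial should help identify the dose most likely to succeed in Phase III, so a wrong figure for the top dose would carry into that choice. It would also carry into the safety record that the DSMB reviews for the arm.

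**Working it through.** **Inputs.** Drug concentration 100 µg/mL (section 5.1; the label's 0.1 mg/mL is the same). Diluent volumes, measured aliquots and the 0.3 mL injection volume are from section 5.4 and Table 3. The vial fill V is 0.5 mL (text) or 0.35 mL (label, if that is the fill).

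**Formula.** Dose = 100 × V_drug / (V_drug + V_diluent) × 0.3.

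**Reproducing Table 3**

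- Level 1: 30 µg / 9.0 mL = 3.33 µg/mL; × 0.3 = 1.0 µg; dilution 1:30.
- Level 2: 30 µg / 3.0 mL = 10 µg/mL; × 0.3 = 3.0 µg; dilution 1:10.
- Level 3, V = 0.5: 50 µg / 1.5 mL = 33.3 µg/mL; × 0.3 = 10.0 µg; dilution 1:3.

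All three rows are correct from their stated inputs.

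**Level 3 at other fills**

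- V = 0.35 (label figure): 35 µg / 1.35 mL = 25.9 µg/mL; × 0.3 = 7.78 µg, which is 22.2% below 10 µg. Dilution 1.35 / 0.35 = 3.86. The step up from Level 2 is 7.78 / 3 = 2.6-fold instead of 10 / 3 = 3.3-fold.
- Assumed values in between: 8.57 µg at 0.40 mL and 9.31 µg at 0.45 mL.

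Levels 1 and 2 and placebo need only 0.3 mL to be withdrawable, which either figure allows.

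**Can Table 3 show which figure is the fill?** It allows up to 4 syringes at Level 3. A total of 1.5 mL is 5.0 injection volumes and 1.35 mL is 4.5, so both permit four. The count does not decide the matter.

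**Measured alternative.** 0.3 mL drug + 0.6 mL diluent: 30 µg / 0.9 mL = 33.3 µg/mL; × 0.3 = 10.0 µg under either reading. With an assumed 0.01 mL misreading of the drug aliquot, 29 / 0.89 × 0.3 = 9.8 µg and 31 / 0.91 × 0.3 = 10.2 µg.

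**Yield of the alternative.** The protocol states no dead volume. Upper bounds follow from the syringe counts:

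- 10 mL vial: 9 − 26 × 0.3 = 1.2 mL at Level 1 and 3 − 6 × 0.3 = 1.2 mL at Level 2. If those counts are true maxima, one more syringe was not possible, so the loss lies above 0.9 mL and up to 1.2 mL. That leaves no dose from 0.9 mL.
- 2 mL drug vial: 1.5 − 4 × 0.3 = 0.3 mL at most. If a new small vial behaves alike, (0.9 − 0.3) / 0.3 = 2 syringes.

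**Drug vials for 25 subjects, at 4 per vial now and 2 per vial proposed**

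- One subject per preparation: 25 and 25, no extra.
- Full batching: 25 / 4 rounds up to 7, and 25 / 2 rounds up to 13; 6 extra.
- Batches of three (eight batches and one single): 8 + 1 = 9, and 8 × 2 + 1 = 17; 8 extra.

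The extra is therefore 0 to 8 vials. Section 5.1 requires injection immediately after dilution, which limits batching.

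**The case against.** The strongest reply is that the protocol states the fill directly and more than once, and the label does not contradict it. Sections 1.2 and 5.1 give the mass as well as the volume. At the label's own concentration, 50 µg requires 0.5 mL, while 0.35 mL would hold only 35 µg. The 7.8 µg scenario therefore needs both the repeated volume and the stated mass to be wrong. The procedures also fit a 0.5 mL fill with 0.35 mL extractable: the measured draws are 0.3 mL, and dilution inside the vial includes any liquid that cannot be withdrawn. This argument stands, and it makes the extractable reading the likelier one.

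It does not close the question. The protocol uses the term extractable only for the diluent: "The diluent is supplied in 50 mL vials with extractable volume 40 mL". The diluent label prints that same 40 mL, which supports the reading, but section 5.1 describes 40 mL as what the diluent vials are filled with. The parallel is only partial.

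A second reply is that changing the preparation is unnecessary if the fill is 0.5 mL. That is accepted, and the change is conditional in the fix. A third is that the consequence is small even on the less favourable reading. That also stands: section 7.2 compares each dose with placebo by a contrast and does not model dose as a quantity, the order of the doses is kept, and the error would be towards less drug.

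**Conclusion.** Minor. The mismatch between text and labels is certain and unexplained, and confidence in that part is high. Its possible effect is confined to Dose Level 3: no effect if 0.5 mL is the fill, and 7.8 µg in place of 10 µg if 0.35 mL is. The second figure assumes that the label volume is the true fill and that 100 µg/mL is correct.

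A reader might infer that the 10 µg arm is under-dosed by 22%, or that Table 3 is miscalculated. The documents support neither. Table 3 is right from its inputs, and the stated mass and repeated volume favour a 0.5 mL fill. Under-dosing is possible but not shown. The plan leaves its top dose resting on a volume that its own labels put in doubt, and one enquiry can settle it.

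**What to change.** Section 3 describes 10 µg enrolment as still to begin. Before it does:

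1. Confirm the fill volume and the extractable volume of the drug and placebo vials with the manufacturer. State both in section 5.1, and correct or explain the 0.35 mL in section 5.7. This costs one query and a few lines of text.
2. If a 0.5 mL fill is not confirmed, prepare Dose Level 3 from a measured aliquot, as at Levels 1 and 2: 0.3 mL entolimod plus 0.6 mL diluent, injecting 0.3 mL. Use a small empty sterile vial of about 2 mL, because the 10 mL vial probably retains more than the 0.9 mL prepared. Change the Table 3 row to 0.6 mL diluent, 0.3 mL drug, 0.9 mL total and up to 2 syringes, once that yield has been checked with the chosen vial.

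If 0.5 mL is confirmed, the present method already gives 10 µg and step 2 is optional; it would only remove the dependence on fill.

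Step 2 costs a supply of small vials and about half the syringes per drug vial, hence the 0 to 8 extra drug vials for the arm. Neither step adds subjects or study procedures.

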5.5 Subject Compliance Monitoring

Subject adherence to the study treatment will be monitored by requiring the subjects to have the study medication administered on-site in the Clinical Research and Trials Unit (CRTU). Records of study medication administration will be documented. Drug accountability will be noted.

5.6 Prior and Concomitant Therapy

Prior/concomitant medications will be assessed at every visit including remote visits.

5.7 Packaging

Entolimod, placebo and diluent will be shipped under cold conditions to the site in cardboard boxes containing 10 single-use vials per box placed into foam inserts. Entolimod vials should remain in the boxes in which they are supplied or stored in a manner that prevents glass-to-glass contact.

Both packaging boxes and individual vials will be labeled with the liquid contents, date of manufacture, lot number, manufacturer information, storage requirements, Mayo Clinic's IRB number, the name of the PI and the federal investigational new drug use warning. See Figure 3.

Figure 3. Labels for Experimental Study Drug Vials and Secondary Shipment Packages.

Labels for entolimod vials

Solution for Injection 0.1 mg/mL Entolimod, 0.35 mL
 Date of Manufacture: 22 AUG 2011
 Lot Number: [REDACTED]
 Manufactured by: Wacker Biotech B.V. (former SynCo Bio Partners B.V. Amsterdam, Netherlands)
 Store at: -70°C
 Mayo Clinic IRB # 19-004847;
 [name]
Refer to Clinical Protocol for Dosing
Caution – New Drug Limited By Federal Law To Investigational Use

Labels for secondary entolimod package

Solution for Injection 0.1 mg/mL Entolimod, 0.35 mL
 Date of Manufacture: 22 AUG 2011
 Lot Number: [REDACTED]
 Manufactured by: Wacker Biotech B.V. (former SynCo Bio Partners B.V. Amsterdam, Netherlands)
 Store at: -70°C
 Mayo Clinic IRB # 19-004847;
 [name]
 Amount in Box: 10 vials
Refer to Clinical Protocol for Dosing
Caution – New Drug Limited By Federal Law To Investigational Use

Labels for entolimod placebo vials

Solution for Injection Entolimod Placebo, 0.35 mL
 Date of Manufacture: 18 AUG 2011
 Lot Number: [REDACTED]
 Manufactured by: Wacker Biotech B.V. (former SynCo Bio Partners B.V. Amsterdam, Netherlands)
 Store at: -70°C
 Mayo Clinic IRB # 19-004847;
 [name]
Refer to Clinical Protocol for Dosing
Caution – New Drug Limited By Federal Law To Investigational Use

Labels for secondary entolimod placebo package

Solution for Injection Entolimod Placebo, 0.35 mL
 Date of Manufacture: 18 AUG 2011
 Lot Number: [REDACTED]
 Manufactured by: Wacker Biotech B.V. (former SynCo Bio Partners B.V. Amsterdam, Netherlands)
 Store at: -70°C
 Mayo Clinic IRB # 19-004847;
 [name]
 Amount in Box: 10 vials
Refer to Clinical Protocol for Dosing
Caution – New Drug Limited By Federal Law To Investigational Use

Labels for entolimod diluent vials

Entolimod sterile diluent, 40 mL per single use vial
 Date of Manufacture: 25 MAR 2016
 Lot Number: [REDACTED]
 Manufactured by: AMRI (Glasgow, United Kingdom)
 Store at: 2-8°C
 Mayo Clinic IRB # 19-004847; [name]
Refer to Clinical Protocol for Use
Caution – New Drug Limited By Federal Law To Investigational Use

Labels for entolimod diluent package

Entolimod sterile diluent, 40 mL per single use vial
 Date of Manufacture: 25 MAR 2016
 Lot Number: [REDACTED]
 Manufactured by: AMRI (Glasgow, United Kingdom)
 Store at: 2-8°C
 Mayo Clinic IRB # 19-004847; [name]
 Amount in Box: 10 vials
Refer to Clinical Protocol for Use
Caution – New Drug Limited By Federal Law To Investigational Use

5.8 Masking/Blinding of Study

In order to minimize the study bias, this study will use a process for randomized assignment to entolimod or placebo. The investigational drug blind will be maintained using the Research Pharmacy processes for preparation of the investigational product. All subjects and study personnel except for those directly involved with study drug preparation will be blinded to study

drug assignment for the entire study. All unblinded dosing information must be maintained in a secured area, accessible only by unblinded personnel.

5.9 Receiving, Storage, Dispensing and Return

5.9.1 Receipt of Drug Supplies

Per GPI request entolimod (study drug), entolimod placebo and entolimod diluent will be shipped overnight to Mayo Clinic from Almac (Souderton PA), clinical storage and distribution facility. Entolimod and entolimod placebo will be shipped on dry ice. Entolimod diluent will be shipped on cold packs. Temperature monitors will be enclosed in all packages.

5.9.2 Storage

All study medication will be provided by GPI. Mayo Clinic Research Pharmacy will be responsible for the storage of medication. The storage condition for the study drug will be described on the medication label. Medication must be stored in a safe, secure location with limited access.

5.9.3 Dispensing of Study Drug

The study drug is to be used exclusively in the clinical study according to the instructions of this protocol and directions for use. The Investigator's designee is responsible for providing subjects with the study drug and instructions for dosing and proper storage of the study drug.

The Investigator's designee will record the amount of study drug dispensed and date of dispensing.

5.9.4 Return or Destruction of Study Drug

At the completion of the study, there will be a final reconciliation of drug shipped, drug dispensed, drug returns, and drug remaining. This reconciliation will be logged on the drug reconciliation form, signed and dated. Any discrepancies noted will be documented and investigated, prior to return or destruction of unused study drug. Drug destroyed on site will be documented in the study files.

6 Study Procedures

The specific study procedures and time of activities to be conducted for each subject enrolled in the study are presented in tabular form in Table S-1.

Physical examinations, other clinical evaluations, and additional laboratory studies or more frequent assessments may be performed consistent with appropriate medical care for the subject, but these data will not necessarily be collected.

In order to optimize scheduling convenience for the subject and for the study center staff, screening procedures may be performed over as many days as necessary within the specified screening period. For scheduled visits and follow-up periods the permitted visit windows are indicated in the table.

For procedures to be performed at a specified time post-dose, the acceptable margin for actual time is the specified time \pm 10 minutes. If multiple procedures are to be done at the same time point, the preferred order is vital signs, blood sampling, and then ECG, with blood sampling (particularly for pharmacodynamics) occurring as close as possible to the specified time.

Missed procedures or evaluations should be performed as close to the originally scheduled date/time as possible. Based on the investigator's judgment, an exception can be made when rescheduling becomes medically unnecessary because it is too close in time to the next scheduled procedure or evaluation. In that case, the missed evaluation may be omitted.

